1.2 Study objectives and endpoints

1.2.1 Primary objective

To demonstrate that early treatment with secukinumab 300 mg s.c. (Arm A1) is superior to standard of care treatment with nb-UVB (Arm B1) in subjects with new-onset moderate to severe plaque psoriasis with respect to subjects achieving \geq 90% improvement (reduction) in psoriasis area and severity index (PASI 90) response at Week 52.

[figure not shown]
1.2.2 Key secondary objective

To evaluate the superiority of early treatment with secukinumab (Arm A1) versus nb-UVB (Arm B1) based on the proportion of all randomized subjects who achieve at least PASI 90 at Week 104.

[figure not shown]
1.2.3 Additional secondary objective

[figure not shown]
To evaluate the effects of early treatment with secukinumab (Arm A1) compared with nb-UVB (Arm B1) based on the proportion of all randomized subjects who achieve at least investigator's global assessment (IGA mod 2011) 0/1 response at Week 52.

1.2.4 Exploratory objectives

4. To explore the effects of treatment with secukinumab compared with nb-UVB based on the proportion of subjects who achieve at least investigator's global assessment (IGA mod 2011) 0/1 response at Week 104

2 Statistical methods

2.1 Data analysis general information

Data will be analyzed using the Statistical Analysis Software (SAS) Version 9.4 or higher, according to the data analysis section (Section 9) of the protocol. This information will also be available in Appendix 16.1.1 of the Clinical Study Report (CSR). Additional important information as appropriate will be given in listings and the CSR. Final study CSR document will include the reports of Main study, mechanistic study and additional analysis.

Unless otherwise specified, the statistical hypothesis tests will be conducted against 1-sided alternative hypothesis, employing a 2.5% level of significance. For other analyses, p-values will be presented as 2-sided, employing a 5% level of significance. Two-sided 95% confidence intervals will be displayed.

Efficacy, safety, and other data will be summarized descriptively as follows:

- for continuous variables, descriptive summary statistics (number of subjects (n), mean, standard deviation (SD), median, minimum, maximum and lower/upper quartiles) for absolute and change (absolute and relative) from Baseline values will be reported by treatment arms (of the Main Study and of the Mechanistic Sub-study, as applicable).
- for categorical variables, frequency (n) and percentage (%) will be presented by treatment arms (of the Main Study and of the Mechanistic Sub-study, as applicable). Percentages will be calculated with respect to the number of evaluable subjects (m) out of the total number of subjects in the analysis set (N) of interest.

For Mechanistic Sub-study at time of final analysis or Week 104 interim analysis (if required) treatment arms are presented by duration of psoriasis for each treatment arm separately as;

New-onset : Arm A1b , Arm A2 and Arm B1b.

Chronic : Arm C1 and Arm C2

Total (wherever required).

In Main Study, after Week 104 subjects continued into the study are low, hence if statistical analysis where missing data is handled using Imputation method then analysis will be performed upto Week 104 unless mentioned otherwise. However, In Mechanistic Sub-study

due to limited number of subjects after Week 104 , listings will be only provided including disposition summary for the final analysis.

2.1.1 General definitions

2.1.1.1 Study treatment

2.1.1.1.1 Investigational and control drugs

Study treatment

Secukinumab (AIN457) 300 mg will be administered in an open-label fashion according to label as 2 s.c. injections of secukinumab 150 mg (1-mL liquid formulation in a pre-filled syringe). Each 300-mg dose will be provided as 2 pre-filled syringes of 150-mg secukinumab in a single box. Each syringe is labeled as AIN457 150 mg/1 mL.

Reference treatment

Narrow-band UVB applied in 1 or 2 cycles, each comprising a period of 12 weeks with 2 to 3 treatment sessions per week totaling 24 to 36 sessions per cycle. The application will be performed according to the investigational site's protocol, taking into account the subject's skin type. A maximum dose of 3 J/cm² on the body and 1 J/cm² on the face is recommended.

Additional treatment

The subjects in Arm B1 may use topical treatment with calcipotriol 50 µg/g and betamethasone 0.5 mg/g applied once daily (50 grams will be the maximum amount that can be applied per week) in addition to nb-UVB during the first 4 weeks of each cycle.

2.1.1.2 Study day

The day of first dose administration of the randomized treatment (Visit 1) will be considered as study day 1. All other study day will be labeled relative to study day 1. The descriptor "study day 0" will not be used.

The day for a particular event on or after the study day 1 will be calculated as:

$(\text{Date of event}) - (\text{Date of first dose}) + 1.$

For example study day 2, study day 3 ... will be one day, two days... after study day 1, and respectively.

During the Screening phase the day before study day 1 will be calculated as:

$(\text{Date of event}) - (\text{Date of first dose}).$

For example study day -1, study day -2,..., will be one day, two days,..., before study day 1 respectively.

2.1.1.3 Screening, Baseline, and post-Baseline assessments

Screening refers to any procedures (e.g., checking inclusion and exclusion criteria) performed prior to the date of first dose of study treatment (for safety analysis) or prior to the randomization date (for efficacy analysis). Per protocol, subject informed consent must be obtained prior to

performing any study related activity. The date of signing informed consent is the start date of Screening period. Any assessment obtained during the Screening period will be labeled as Screening assessment. Assessments made on Day 1 may occur before or after the randomization or the first dose. Further information will be found in [Study Programming Dataset Specifications \(PDS\)](#).

For both efficacy and safety analyses, Baseline assessments are defined as the last assessment (including unscheduled assessment) taken on or before the first dose of randomized study treatment, which is typically the last assessment taken before study drug administration at Visit 1. If the Baseline assessments are missing, then the last available measurement on or before the first dose of randomized study treatment (that is from the Screening visit, if available) will be considered as Baseline.

All the assessments taken after first dose of study treatment will be considered as post- Baseline assessments.

2.1.1.4 Day of last dose of randomized study treatment

The date of last dose will be collected via the eCRF. The subject's exposure will be calculated considering the last visit or the last dose + 84 days whichever occurs earlier.

For safety analysis on-treatment is defined as assessments from the first dose to last dose plus 84 days.

2.1.1.5 Visit windows

Visit-windows will be used for the data that is summarized by visit; they are based on the study evaluation schedule and comprise a set of days around the nominal visit day. For any assessment, there are the protocol defined scheduled visits around which visit windows were created to cover the complete range of days within the study. The visit windows are shown in [Table 2-1](#). These apply to measurements taken at every visit. For assessments collected less often different visit windows will be applied as detailed below.

When visit windows are used, all visits will be re-aligned, i.e., they will be mapped into one of the visit windows. E.g., if the Week 16 visit of a subject is delayed and occurs on Day 146 instead of on Day 129, say, it will be re -aligned to visit window Week 24. In the case of major deviations from the visit schedule, or due to unscheduled visits, several assessments of a subject may fall in a particular visit window (either scheduled or unscheduled). Statistical approaches to handle multiple assessments in a given visit window are specified in [Section 2.1.1.5.1](#).

In general, if 2 consecutive visits V_t and V_s are x days apart, the upper limit of the visit window for V_t will be $V_t+x/2$ and the lower limit for the visit V_s will be $V_s-x/2$ (if x is even, the lower limit for V_s will be $V_s-x/2+1$, and the upper limit for V_t will be $V_t+x/2$). The algorithm needs to ensure that visit windows are not overlapping and that there are no gaps, such that each assessment can be uniquely allocated to one visit window, e.g., if Week 16 visit is scheduled for day 113, Week 24 is scheduled at day 169 and Week 36 is scheduled at day 253, then the visit window for Week 24 extends from Day 142 to Day 211. Of note, subjects are allowed to have gaps in visits.

Table 2-1 Assessment windows for scheduled visits

Treatment Arms	Analysis visit	Week	Scheduled day	Visit Window
ALL: A1, B1, A2, C1 and C2	Baseline	BL	1	-28 days to Day 1
	Week 16	16	113	Day 2-141
	Week 24	24	169	Day 142-211
	Week 36	36	253	Day 212-309
	Week 52	52	365	Day 310 – 421*/407*
A2 and C2 only	Week 68	68	477	Day 422-533
	Week 84	84	589	Day 534-645
	Week 100	100	701	Day 646-715
	Week 104	104	729	Day 716-771**
A1 and B1 only	Week 64	64	449	Day 408-491
	Week 76	76	533	Day 492-575
	Week 88	88	617	Day 576-659
	Week 100	100	701	Day 660-715
A1, B1 only Arm A2 from Week 105 on	Week 104	104	729	Day 716-771
	Week 116	116	813	Day 772-855
	Week 128	128	897	Day 856-939
	Week 140	140	981	Day 940-1023
	Week 152	152	1065	Day 1024-1107
	Week 164	164	1149	Day 1108-1191
	Week 176	176	1233	Day 1192-1275
	Week 188	188	1317	Day 1276-1359
	Week 200	200	1401	Day 1360-1443
Week 208/EOS	208	1457	Day 1444-1541***	

* For Arm C1, If a visit falls after the last visit window (after Day 421) it is not assigned an analysis visit and will be listed under label “After Week 52”.

*For Arm A1 and B1, the Week 52 visit window will have 407 as a upper limit days

*For Arm A2 and C2, the Week 52 visit window will have 421 as a upper limit days

** For Arm C2, If a visit falls after the last visit window (after Day 771) it is not assigned an analysis visit and will be listed under label “After Week 104”.

*** For Arms A1, A2 and B1, If a visit falls after the last visit window (after Day 1541) it is not assigned an analysis visit and will be listed under label “After Week 208”.

The following visit window convention will be followed for schedule for the collection of skin biopsies (Table 2-2). Assessments, performed between the visits windows, will only be listed.

Table 2-2 Assessment windows for skin biopsies

Treatment Arms	Analysis visit	Week	Scheduled day	Visit Window
A1b, B1b, A2, C1 and C2	Baseline	BL	1	-28 days to Day 1
	Week 16	16	113	Day 99-141
	Week 52	52	365	Day 337-393
A1b, B1b, A2, and C2	Week 104	104	729	Day 701-757
A1b, B1b, and A2	Week 208	208	1457	1429-1541

2.1.1.5.1 Multiple assessments within visit windows

When there are multiple assessments in a particular visit window, the following rules are applied to select one value “representing” the subject in summary statistics in a visit window.

For Baseline assessment definition see [Section 2.1.1.3](#).

For post-Baseline visit windows the following applies (unless otherwise specified):

- for quantitative variables, the closest to the actual visit is chosen (if 2 assessments have the same distance, then the earlier one will be chosen);
- for qualitative variables, the worst record is selected. It is noted that in the analyses performed, worst case is always well defined (e.g., for urine protein values “+” and “++”, the worst case is defined as “++”),
- in case qualitative variables are based on quantitative variables, e.g. PASI 90 response, the visit will be assigned to the quantitative variable, and this visit will be used for the derived qualitative variable.

Table 2-3 Rules for selecting values for analysis within a given visit window

Timing of measurement	Type of data	Rule
Baseline	All data	See Section 2.1.1.2 .
Post-baseline efficacy	All data except for ████	The measurement closest to the target day will be used. In the event 2 measurements are taken equally apart (e.g., 1 day before target date and 1 day after), the earlier one will be used. If 2 measurements are taken on the same day, then select the first one using eCRF visit number. If 2 measurements have been taken on the same day and same visit then select the worst.

Timing of measurement	Type of data	Rule
[REDACTED]	[REDACTED]	[REDACTED]
Post-baseline safety	Summary visit information (e.g. lab, ECG, etc.)	
The (non-missing) measurement closest to the target day will be used.
 
In the event 2 measurements are taken equally apart (e.g. 1 day before target date and 1 day after) the first one will be used.
 
If 2 measurements are taken on the same day then select the first one (using the time).
 
If 2 measurements are taken on the same date/time then use the first visit number (assuming this is the planned visit).
 
If 2 measurements are taken on the same date/time/eCRF visit number then use the average of 2 assessments

Post-baseline safety	Notable abnormalities (e.g. vital signs) and CTCAE grading for laboratory values	The most extreme measurement in the window will be used. Note this means a subject can have a notably high and notably low measurement within an analysis period

2.2 Analysis sets

The following analysis sets will be used:

Randomized set: The randomized set will be defined as all subjects who were randomized at Baseline Visit. Unless otherwise specified, misrandomized subjects will be excluded from the randomized set.

Misrandomized subjects are subjects who are screen failures, but have been randomized by the investigator before eligibility was finally assessed, however have not been treated. If subjects were re-screened and successfully randomized, they will be included in the randomized set according to the treatment assigned in the last randomization.

Full analysis set (FAS): The FAS will be comprised of all subjects who were randomized to the study. Following the intent-to-treat principle, subjects will be analyzed according to the treatment assigned at Baseline.

Modified full analysis set (mFAS): The mFAS includes all subjects who are randomized and took at least one dose of study treatment during the Treatment Phase, subjects will be analyzed according to the treatment assigned at Baseline.

Safety set (SAF): The safety set includes all subjects who took at least one dose of study treatment during the Treatment Phase, whether or not they were randomized. Subjects will be analyzed according to the treatment received.

[Section 2.15.2](#) define the analysis set used for additional analysis.

Protocol deviations leading to exclusion from analysis sets are defined in Section 5.7.

The treatment arms for the analyses of data will have the following distribution of subjects:

Main Study (Planned number)

- Eighty subjects from Arm A1 (i.e., A1a(68)+A1b(12))
- Eighty subjects from Arm B1 (i.e., B1a(68)+B1b(12))

Mechanistic Sub-study (Planned number)

- Twelve subjects from ArmA1b
- Twelve subjects from Arm A2
- Twelve subjects from Arm B1b
- Twelve subjects from Arm C1
- Twelve subjects from Arm C2

2.2.1 Subgroups of interest

The following subgroups of analysis will be explored for the primary and the key secondary analysis (Arms A1 and B1) :

- Weight (≤ 90 kg, >90 kg)
- BMI (< 25 , $25-< 30$, ≥ 30)
- Onset of psoriasis time (0-6 months, 6-12 months)
- Age ($< 18-30$, $31-50$)
- Concomitant medication in UVB arm (yes, no)
- Previous psoriasis therapy (biologic systemic therapy, non-biologic systemic therapy , Topical, phototherapy and Photochemotherapy – yes/no)

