5.1.2 Additional treatment

The patients in Arm B will be allowed to use topical treatment with calcipotriol 50 µg/g and betamethasone 0.5 mg/g applied once daily (50 grams will be the maximum amount that can be applied per week) in addition to nb-UVB only during the first 4 weeks of each cycle.

The topical cream will be used as per the sites' standard procedure and as per the expert opinion of the principal investigator.

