5.5.8 Prohibited medication

Use of the treatments displayed in [Table 5-1](#) and [Table 5-2](#) is NOT allowed after baseline.

No other treatments for psoriasis than the study treatments and the additional use of calcipotriol 50 µg/g and betamethasone 0.5 mg/g during the first 4 weeks in Arm B1 will be allowed during the Treatment Epoch. Bland emollients and topical glucocorticosteroid treatments of mild to moderate potency on the face, scalp, and/or genitoanal area for Arm A1, Arm A2, Arm B1, Arm C1, and Arm C2 are an exception. Exposure to UV light (e.g., sunbathing and/or the use of tanning devices) other than nb-UVB within the study, from enrollment to Week 104 of the study should be limited. Mild to moderate potency topical glucocorticosteroids will be allowed during the Follow-up Epoch.

Table 5-1 Prohibited treatment (Arm A1, Arm A2 and Arm B1)

Prohibited treatments ^{a, b}	Washout period (before baseline)
Secukinumab	No prior use allowed
Any biologic drug directly targeting IL-17A or the IL-17 receptor (other than secukinumab, e.g., brodalumab, ixekizumab)	No prior use allowed
Alefacept, briakinumab, efalizumab	No prior use allowed
Biological immunomodulatory agents other than the above listed (e.g., adalimumab, etanercept, infliximab)	No prior use allowed
Other systemic immunomodulatory treatments ^c (e.g., methotrexate, cyclosporine A, glucocorticosteroids [oral, i.v., intramuscular, s.c., intra-articular, transdermal], cyclophosphamide) and any treatment for psoriatic arthritis, except for NSAIDs	No prior use allowed
Any biologic drug directly targeting IL-12/IL-23 other than ustekinumab or IL-23 (e.g., guselkumab, tildrakizumab)	No prior use allowed
Other systemic psoriasis treatments (e.g., retinoids, fumarates, apremilast)	No prior use allowed
Photo-chemotherapy (e.g., psoralen plus UVA [PUVA]) or phototherapy ^d	No prior use allowed
Topical treatment that is likely to impact signs and symptoms of psoriasis (e.g., vitamin D analogues, pimecrolimus, retinoids, Salicyl-Vaseline, salicylic acid, lactic acid, tacrolimus, tar, urea, α -hydroxy or fruit acids) ^e	2 weeks
Live virus vaccinations	6 weeks
Any investigational treatment or participation in any interventional study	4 weeks or 5 half-lives (whichever is longer)

NSAID = nonsteroidal anti-inflammatory drug, UVA = ultraviolet light A

a) If the prohibited treatment is used during the study for any indication, patients must discontinue its use if they wish to continue in the study

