- **Arm B1:** Subjects with new-onset plaque psoriasis will receive either 1 or 2 cycles of nb-UVB of 12 weeks each with a maximum break of 28 weeks between cycles (subjects with PASI 90 at Week 40 will not receive a second treatment cycle). Only during the first 4 weeks of each cycle, nb-UVB treatment will be given in combination with topical calcipotriol 50 µg/g and betamethasone 0.5 mg/g.

Follow-up Phase

At the end of the Treatment Phase at Week 52, all subjects with \geq PASI 50 response from Arm A1 and Arm B1 will enter the Follow-up Phase. Subjects who do not achieve a PASI 50 response, will have all assessments of end of study (EOS) and be discontinued from the study.

[figure not shown]
During the Follow-up Phase, subjects will not receive study treatment; they will be observed maximally until Week 208, and compared regarding the proportion of them who achieve PASI 90 response at Week 104.

Subjects who relapse (those who experience a loss of 50% of the maximum improvement in PASI score achieved during the Treatment Phase) will have all assessments of EOS and be discontinued from the study.

If no relapse occurs, subjects who achieve $<$ PASI 90 at Week 52 in Arms A1 (A1a and A1b) and B1 (B1a and B1b) will be followed until Week 104, while subjects who achieve \geq PASI 90 at Week 52 will be followed until Week 208.

The investigator should provide ongoing adequate care for subjects who relapse. If the investigator decides to continue treating the subjects with secukinumab, a new loading dose of commercially available secukinumab could be considered. The treatment with secukinumab after relapse will be out of scope of the study.

Figure 1-1 Study design – Main study

BL = baseline, EOS = end of study, KSE = key secondary endpoint, nb-UVB=narrow-band ultraviolet B, PASI = psoriasis area and severity index, PE = primary endpoint, R = randomization.

Mechanistic Sub-study

A separate informed consent will be obtained from study subjects who agree on having skin biopsies taken and therefore become eligible for this Mechanistic Sub-study. Besides the biopsies, subjects will undergo the same assessments as in the Main Study.

Treatment Phase

At the Baseline Visit, eligible subjects will be allocated to one of the treatment arms of the mechanistic Sub-study (see [Figure 1-1](#)):

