2.4.2 Prior and concomitant medications

Prior treatments are defined as treatments taken and stopped prior to the first dose of study treatment.

Any treatment given at least once between the day of first dose of randomized study treatment (Baseline) and 84 days after the last dose of study treatment or last visit (including follow-up visits) will be a concomitant treatment, including those which were started pre-Baseline and continued into the Treatment Phase.

Concomitant medications and prior medications taken within the 6 months preceding study enrollment will be captured at the Screening visit, and updated at Baseline, with ongoing or not ongoing information. Prior or concomitant medication will be identified based on recorded or imputed start and end dates of medication taken. Further rules are given in section 5.3.3.

Prior and concomitant treatments will be summarized by treatment arms in separate tables for the SAF and for the Treatment Phase and follow-up period, separately. Treatments will be presented in alphabetical order, by ATC codes and grouped by anatomical main group (the 1st level of the ATC codes). Tables will also show the overall number and percentage of subjects receiving at least one treatment of a particular ATC code and at least one treatment in a particular anatomical main group.

In addition, previous psoriasis therapy

- any “previous < biologic systemic /non-biologic systemic> therapy” (yes/no)
- previous biologic systemic therapy (yes/no, with embedded subgroup “Failure”* – yes/no),
- previous non biologic systemic therapy (yes/no, with embedded subgroup “Failure”* – yes/no),
- Previous topical (yes/no), previous phototherapy (yes/no), previous photochemotherapy (yes/no) and
- “Failure to at least 2 previous psoriasis therapy (biologic systemic, non-biologic systemic, topical, phototherapy and photochemotherapy)” (yes/no will also be summarized in a similar manner.

(* at least one therapy with lack of primary efficacy or lack of secondary efficacy or lack of tolerability).

In addition, medical procedures and significant non-drug therapies as coded in MedDRA will be summarized. “Surgical and Medical Procedures” eCRF page will be used to get this information. Concomitant Medications - Topical Corticosteroid will also be summarized similarly. Concomitant Medications - Topical Corticosteroid eCRF page will be used to get this information.

Previous psoriasis therapy will be available for chronic subjects only.

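### A subgroup of the A1 v B1 comparison is defined after randomization and for the nb-UVB arm only, so a contrast by it is not randomized and is open to confounding

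*SAP*

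**What the plan says.** SAP 2.2.1 opens its list as follows: "The following subgroups of analysis will be explored for the primary and the key secondary analysis (Arms A1 and B1"). As labelled, five of the six factors (weight, BMI, time since onset, age, previous psoriasis therapy) are fixed before treatment and apply to either arm. The remaining one is "Concomitant medication in UVB arm (yes, no"). The visible text does not say which medication counts, over which period, or how A1 patients are placed.

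Other sections bear on it:

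- **Timing.** SAP 2.4.2 defines concomitant treatment in these terms: "Any treatment given at least once between the day of first dose of randomized study treatment (Baseline) and 84 days after the last dose". Its window can also run to the final visit, follow-up included.
- **Availability.** Protocol 5.1.2 allows calcipotriol/betamethasone in Arm B, "in addition to nb-UVB only during the first 4 weeks of each cycle". Protocol 5.5.4 has its use recorded on the Concomitant Medication eCRF page.
- **Who decides.** Protocol 5.1.2 leaves use to each site's "standard procedure and as per the expert opinion of the principal investigator".
- **Second cycle.** SAP 1.1 states that "subjects with PASI 90 at Week 40 will not receive a second treatment cycle".
- **Other topicals.** Protocol 5.5.8 makes an exception for "Bland emollients and topical glucocorticosteroid treatments of mild to moderate potency on the face, scalp, and/or genitoanal area for Arm A1" and for the other arms.
- **Carry-over.** SAP 2.5.2 expects no influence on the primary analysis from topical use in the first 4 weeks, because the effect will have gone by Week 52.

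**The concern.** A subgroup contrast keeps the protection of randomization when the factor is fixed before randomization and defined the same way in both arms. This factor meets neither condition.

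An output that follows the list would show two A1 v B1 differences, one at each level. A reader would naturally take the gap between them as showing how far the advantage of secukinumab depends on whether nb-UVB was given with a topical. The design cannot support that conclusion, because the gap may reflect who was given the topical and not what the topical did.

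**Working it through.** **1. The plan's own figures.** The subgroup has no stated figure, so the check starts from the full comparison.

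- Primary (SAP section 3): 80 per arm, 70% v 28%, one-sided 0.025, stated power 99.9%. Unpooled Wald: SE = √(0.70×0.30/80 + 0.28×0.72/80) = 0.0717; 0.42/0.0717 − 1.96 = 3.90; power 99.995%. With the pooled variance under the null it is 99.989%. Reproduced.
- Key secondary (Protocol 9.9): 21% v 4%, one-sided Fisher's exact test, stated power about 89%. Exact enumeration gives 90.0%. Reproduced within about one point.

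Both concern all randomized A1 and B1 patients and do not involve the subgroup.

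**2. Can A1 be classified?** The label confines the factor to the UVB arm, and the add-on topical is available only there. No visible rule assigns A1 patients to yes or no. Each level must therefore use all of A1 or an arbitrary part of it.

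**3. Is use tied to prognosis or response?** Use is chosen by site and investigator in an open-label study (Protocol 5.4). Cycle timing adds a link to response. With a 12-week first cycle and the maximum 28-week break, a second cycle starts at Week 12 + 28 = 40. Patients with PASI 90 at Week 40 do not receive it and so have no second topical window. If yes means use in cycle 2, the link is direct. If it means any use, the link acts only through patients whose first use would have been in cycle 2.

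**4. Does the carry-over statement settle it?** No. It concerns how long a drug effect lasts, not who is selected to receive the drug. A topical window at Weeks 40 to 44 would also end only 52 − 44 = 8 weeks before the primary assessment.

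**5. Simple illustration (assumed rates, no topical effect).** Half of B1 are users, with PASI 90 of 20% in users and 36% in non-users. The B1 mean is (0.20 + 0.36)/2 = 0.28, as planned. Against A1 at 70%: 0.70 − 0.20 = 50 points and 0.70 − 0.36 = 34 points.

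**6. Range over the strength of selection (assumed rates, no topical effect).** Half of patients have a worse prognosis. Response in worse/better prognosis is 14%/42% in B1 (mean 28%) and 60%/80% in A1 (mean 70%). Let s_w and s_b be the proportions using the topical in each group. Then:

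- share with worse prognosis among users: u = s_w/(s_w + s_b)
- B1 response among users: 0.14u + 0.42(1 − u)
- non-users: the same, with 1 − s_w and 1 − s_b in place of s_w and s_b.

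| Use in worse/better prognosis | B1 yes | B1 no | All A1 − B1 yes | All A1 − B1 no |
|---|---|---|---|---|
| 50%/50% | 28.0% | 28.0% | 42.0 | 42.0 |
| 60%/40% | 25.2% | 30.8% | 44.8 | 39.2 |
| 70%/30% | 22.4% | 33.6% | 47.6 | 36.4 |
| 90%/10% | 16.8% | 39.2% | 53.2 | 30.8 |

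In the last row, A1 patients with the same prognostic mix would give differences of 45.2 and 38.8. So 6.4 points of the 22.4-point gap come from the prognostic mix itself, and 22.4 − 6.4 = 16.0 from setting a selected part of B1 against all of A1. If better-prognosis patients use the topical more, the columns swap.

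**The case against.** The disputed contrast has to be inferred. The SAP gives a one-line label, with no visible model, interaction test or estimate by this factor. The mention of both arms may only name the Main Study, and the words about the UVB arm could mean a split within B1. Parts of the SAP's exploratory and change sections are redacted and could hold the method. This limits certainty, but the list's opening sentence attaches every item to the A1 v B1 analyses, so a within-B1 summary is not what the text says.

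Use may also be mostly a matter of site habit, unrelated to individual severity. A reader might infer that the contrast is certainly biased. The documents do not support that: with use unrelated to prognosis the bias is zero. They give no reason to assume such independence either.

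A reader might also infer that A1 has no concomitant topical use at all. Protocol 5.5.8 rules that out, since emollients and limited-site mild to moderate steroids are allowed there. The lack of a counterpart applies to the factor as labelled and to the add-on.

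Finally, the consequence is small. No alpha attaches to any subgroup, and even in the simple illustration A1 leads by 34 points or more. That stands. The SAP change history drops subgroup analysis for the additional analysis, but that refers to the follow-up work in SAP 2.15 and leaves this list in place.

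**Conclusion.** The point holds as a minor one. An A1 v B1 contrast by this factor is not a randomized comparison and is open to confounding in either direction. It rests on the list's heading, the timing and choice of the add-on topical, and the absence of any visible rule for classifying A1.

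The documents give no figure for the size. Only the 70% and 28% means come from the plan. The 50 v 34 points, and the spread from 30.8 to 53.2 around 42, depend on assumed use and response rates and show only what selection alone could produce. They are not estimates of bias in this trial. Nor should anyone infer that the primary or key secondary result is in doubt: the hierarchical tests, their alpha and their power do not use this factor.

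**What to change.** 1. Remove the factor from the A1 v B1 subgroup list in SAP 2.2.1.
2. If the information is wanted, report PASI 90 by add-on topical use descriptively within B1 only, stating which medication counts and over which period or cycle, and label it non-randomized. The period matters: the SAP 2.4.2 definition can run into follow-up, when Protocol 5.5.6 permits topical steroids.
3. Reconcile the passages on the add-on. Protocol 3.1 and 5.1.2 and SAP 2.1.1.1 treat it as optional, Protocol 5.2 says it should be used, and SAP 1.1 presents it as part of each cycle. Under the last wording the no level would be nearly empty.

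The first two steps cost about one line of the SAP and replace one comparative output with a descriptive one. The third is a wording check. If the output already exists, the label can go in the final study report, where the SAP introduction already requires changes to be described.
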